# PROTOCOL TITLE: Micropulse for suppression of diabetic macular edema “PULSE STUDY”

1. Confirm the patient’s identity and eye to be treated using a standard pre-procedure time-out. Confirm the patient’s eye is dilated and comfortably postured at the slitlamp for treatment.
2. Ensure the laser aiming beam is in focus on the retinal surface.
3. Confirm the IQ 577 laser system is in CW treatment mode using the laser’s Preset function. Using a contact lens with an approximate 1x laser magnification for macular laser treatment (e.g. Volk Area Centralis®) and a 200 µm spot, perform the test spot in continuous wave (CW) mode with a 200 ms duration in the minimally edematous macula > 2 DD from foveal center.
4. Start at 50 mW and titrate power upwards in 10 mW increments – moving to a new area each time – until a barely visible tissue reaction is seen. If a reaction is evident with 50 mW, do not increase the power. Note the threshold power.
5. Switch the laser to MicroPulse mode at 5% duty cycle using the laser’s Preset function and adjust the power to 4 times the power achieved in the CW pre-treatment test spot.
6. Deliver a single spot outside the macula to confirm laser system is in MicroPulse mode.
7. Adjust the TxCell Scanning Delivery System to a 7x7 grid with zero-spot spacing.
8. Deliver high-density applications as indicated in FIGURE 1: three 7x7 grids above and below the fovea (250 µm from its center) and one 7x7 grid at each side (temporal and nasal) of the fovea (250 µm from its center); if edema is present outside this area, treat it too.

**FIGURE 1**

TxCell 7 x 7 grid pattern (49 spots)

**PROTOCOL TITLE: Micropulse for suppression of diabetic macular edema  
“PULSE STUDY”**

9. Confirm that the patient can detect at least finger-counting vision after laser procedure.

Those in the sham treatment arm will undergo the same set up procedures as described above, however, no actual laser treatment will occur. Subjects will then return to the clinic for repeat ophthalmic exam, OCT imaging, and microperimetry at 1 month, 3 month, 6 month, 9 month, 12 month, 15 month, 18 month, 21 month and 24 month time points, which is similar in frequency as standard of care. Patients in the treatment arm are eligible for repeat SML laser at any subsequent visit if there is any decline in vision (1 or more ETDRS lines) or worsening in edema (>10% increase), at the discretion of the treating physician. If vision declines to 20/40 or worse at any study visit, patients in the treatment arm will undergo repeat treatment with SML laser, while those in the sham arm will undergo repeat sham laser.

If the patient demonstrated 20/40 or worse ETDRS visual acuity at any study visit, he or she will be required to return within 28 days for repeat ETDRS visual acuity testing, ophthalmic exam, OCT imaging, and microperimetry. If the patient demonstrated 20/40 or worse ETDRS visual acuity at this repeat visit, then the patient will have reached study endpoint and be considered treatment failure. At that visit, patients may be given any combination of intravitreal anti-VEGF injection (preferred based on DRCR.net protocol I and protocol T), focal/grid laser, repeat SML treatment, or intravitreal steroid injection, based on the discretion of the investigator. After study endpoint (visual acuity loss to 20/40 or worse), patients may be treated on a monthly, pro re nata (PRN), or "treat-and-extend" basis based on the individual investigator's preference. Patients are still required to continue with study visits, but any additional visits or treatments, although still documented, will be considered off-study.

All data will be analyzed in accordance to the “intention-to-treat” principle.

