#### **Inclusion Criteria:**

1. Age  $\geq$ 18 years
2. Type 1 or type 2 diabetes mellitus
3. Clinical evidence of center-involved DME confirmed on OCT, and defined by OCT Central Subfield (CSF) thickness at the time of randomization by the following:
  - a. Zeiss Cirrus: 275 $\mu$  in women, and 290 $\mu$  in men
  - b. Heidelberg Spectralis: 290 $\mu$  in women, and 305 $\mu$  in men
4. Best corrected visual acuity of 20/32 or better on ETDRS testing

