**7) Study Timelines**

- The duration of an individual subject’s participation in the study will be two years which will include at least 10 total visits at various time points including on the day of enrollment, followed by 1, 3, 6, 9, and 12, 15, 18, 21, 24 months after the day of enrollment
- The duration anticipated to enroll all study subjects is 1 year
- The estimated date for the investigators to complete this study is December 2023
- 36 eyes will be enrolled based on power calculations for 80% power assuming at least 40% of eyes monitored by observation alone will experience vision loss to 20/40 or worse, and that SML treatment will reduce that value to 15%, using a 2:1 ratio for randomization (2 treatment : 1 observation (sham)). The ETDRS study showed that among eyes with good visual acuity (20/25 or better), 40% will experience a visual acuity decrease by 5 letters or more. We assume a higher rate among eyes with 20/32 or better.

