**8) Study Endpoints**

Primary outcome:

- Proportion of patients with vision loss to 20/40 or worse on ETDRS testing on two visits  $\leq 28$  days apart at 12 and 24 months.
- Mean time to vision loss to 20/40 or worse on ETDRS testing on two visits  $\leq 28$  days apart

Secondary Outcomes:

- Mean change in visual acuity, low luminance visual acuity and contrast sensitivity at 3, 6, 9, 12, 15, 18, 21, and 24 months from baseline
- Mean change in central macular thickness (CMT) on OCT at 3, 6, 9, 12, 15, 18, 21, and 24 months from baseline
- Mean change in retinal sensitivity assessed by microperimetry at 3, 6, 9, 12, 15, 18, 21, and 24 months from baseline
- Percentage of subjects with visual acuity loss (including low luminance visual acuity and contrast sensitivity) of  $\geq 5$  letters at 12 and 24 months
- Percentage of subjects with at least 10 and 15 letter gain or loss at 12 and 24 months
- Visual acuity area under the curve at 12 and 24 months
- Number of SML treatments received at 12 and 24 months
- Number of anti-VEGF treatments received at 12 and 24 months
- *Any safety concerns documented during the study*

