## **PROTOCOL TITLE: Micropulse for suppression of diabetic macular edema “PULSE STUDY”**

### **9) Procedures Involved**

This is a randomized, controlled clinical trial comparing subthreshold micropulse laser versus sham laser treatment for eyes with diabetic macular edema with good visual acuity of 20/32 or better. After signing written consent and enrolling in the study, patients will be randomized to receive either subthreshold micropulse laser treatment or no treatment (sham). Randomization will occur as a ratio of 2:1 and will take place during the clinic visit. A block randomization scheme will be created before the study begins to ensure appropriate treatment allocation among the two groups. At the time of randomization, only one eye will be randomized to either the treatment or observation. If both eyes meet the inclusion criteria, one eye (worse eye) will be assigned to the treatment group and the fellow eye to the sham treatment group. Subjects selected for the study will then undergo a complete ophthalmic examination, including measurements of best corrected visual acuity, low luminance visual acuity, contrast sensitivity (using ETDRS testing with a masked coordinator), intraocular pressure, slit lamp exam including documentation of lens status, and dilated funduscopy exam with standard dilating agents used at the UC Davis Eye Center. Subjects will then undergo baseline imaging with SD-OCT and fundus autofluorescence (FAF) using the Spectralis OCT+SLO instrument (Heidelberg Engineering, Heidelberg, Germany) and Optos (Optos Inc.). The Optos imaging system will only be used as a back up to the Heidelberg, as well as microperimetry testing using Nidek MP-1 instrument (Padova, Italy). Both the use of OCT, FAF, and microperimetry testing are within the standard of care for the management of DME.

For OCT and FAF, a lubricating artificial tear drop may be used on subjects with dry eyes to enhance image quality as is routinely done. Each eye will have 3-4 images acquired, which will take approximately 30-45 seconds for each eye. OCT imaging must include at least one high resolution scan across the fovea, and central macular thickness measured as determined using the OCT instrument's algorithm. FAF imaging must include the entire macular region through which the micropulse laser treatment will be applied.

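### Repeat sham is specified only at 20/40 or worse, while repeat micropulse laser is allowed earlier, so a repeat session in an eye still better than 20/40 could reveal the arm

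*Protocol*

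**What the plan says.** All the retreatment rules are in protocol section 9 (Procedures Involved), in the text after Figure 1.

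- **Day 0.** The arms are matched: "Those in the sham treatment arm will undergo the same set up procedures as described above, however, no actual laser treatment will occur".
- **Early triggers.** "Patients in the treatment arm are eligible for repeat SML laser at any subsequent visit if there is any decline in vision" of one or more ETDRS lines, or "worsening in edema (>10% increase), at the discretion of the treating physician". The sham arm is not mentioned.
- **20/40 or worse.** The arms are matched again. Treatment-arm eyes have repeat SML, "while those in the sham arm will undergo repeat sham laser".
- **Confirmation.** After any reading of 20/40 or worse, the participant returns within 28 days. A second such reading is the study endpoint, after which treatment is open.

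Section 8 makes the first primary outcome "Proportion of patients with vision loss to 20/40 or worse on ETDRS testing on two visits" no more than 28 days apart, assessed at 12 and 24 months. The second is the mean time to that event. Section 9 names acuity testing as done "using ETDRS testing with a masked coordinator", and section 11 has images read masked. Section 7 places visits at enrollment, "followed by 1, 3, 6, 9, and 12, 15, 18, 21, 24 months after the day of enrollment".

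**The concern.** A sham procedure serves to keep participants from knowing their arm. This protocol provides it at day 0 and again at 20/40 or worse. In between, the text gives a further session to SML eyes alone. A participant who is called back to the laser while acuity is still better than 20/40, and who knows how retreatment is decided, could conclude that the eye is in the SML arm.

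This matters because the primary outcomes rest on ETDRS acuity, where the result depends partly on how hard the participant tries. The same holds for several secondary outcomes: low luminance acuity, contrast sensitivity, and microperimetry, in which the participant presses a trigger on seeing the stimulus. A masked coordinator and masked image reading do not hide from the participant that a session took place. The gap lies in a treatment procedure that the protocol itself fixes, so an analysis plan could not repair it.

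**Working it through.** No figure in the protocol has to be reproduced for this point. The check sets the rules side by side by arm, and then asks which eyes and which visits are affected.

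**1. Rules by arm (section 9)**

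| Situation | SML arm | Sham arm | Matched? |
|---|---|---|---|
| Day 0 | SML | Sham set-up, no laser | Yes |
| Loss of ≥1 line, still better than 20/40 | Repeat SML allowed | Nothing specified | No |
| Edema up >10%, still better than 20/40 | Repeat SML allowed | Nothing specified | No |
| 20/40 or worse, first reading | Repeat SML | Repeat sham | Yes |

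No other section of the protocol supplies a repeat sham for the two middle rows.

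**2. Which eyes**

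Entry requires 20/32 or better (section 6). Two assumptions are needed that the protocol does not state: that 20/25, 20/32 and 20/40 are successive lines, and that the decline is counted from entry acuity.

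- Entry 20/25, minus one line = 20/32. This is better than 20/40, so a repeat session is specified under SML only.
- Entry 20/32, minus one line = 20/40. The matched rule applies.

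So the acuity trigger leaves a gap for eyes that enter at 20/25 or better. The edema trigger leaves one for any eye still better than 20/40, whatever its entry acuity.

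**3. Which visits**

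Scheduled follow-up is at months 1, 3, 6, 9, 12, 15, 18, 21 and 24, which is 9 visits.

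- Before the 12-month assessment: months 1, 3, 6, 9 = 4 visits.
- Before the 24-month assessment: months 1 to 21 = 8 visits.

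The rule is not confined to scheduled visits. Take an eye that entered at 20/25 and reads 20/40: both arms have a matched session. At the return visit within 28 days it reads 20/32. It is one line below entry and better than 20/40, so an SML eye may be retreated again and a sham eye has no corresponding session.

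**4. Is early retreatment plausible?**

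Section 14 cites a series in which 15 of 39 SML-treated eyes with DME and acuity better than 20/40 needed retreatment: 15/39 = 38%. Section 7 plans 36 eyes at 2:1, so about 36 × 2/3 = 24 SML eyes, and 24 × 15/39 ≈ 9. This is an illustration only. It assumes that the cited rate carries over to this trial, although the retreatment rule of that series is not given. It shows that such sessions are foreseeable, not how many there will be or what they would do to acuity results.

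**The case against.** The strongest reply is that the chain from repeat session to biased acuity has links the document does not show. A participant who does not know the rule sees only a repeat of the day-0 procedure, which sham eyes also had. What participants are told about retreatment is not in the text available. The protocol calls the acuity coordinator and the reading center masked, but never says so of participants. Retreatment is discretionary, so not being retreated tells a participant little; only retreated SML participants could learn their arm. The endpoint needs two readings of 20/40 or worse, and a matched session is given at the first of them. The protocol also does not forbid repeat sham at the early triggers, and the pairing at 20/40 suggests that matching was intended.

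Most of this stands, and it limits the point. It does not remove it. The sham and its repetition at 20/40 have little purpose unless participants are meant not to know their arm. Staff who follow the text literally would create the mismatch.

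A reader might go further and infer that the trial is unmasked, or that the result is biased in favor of SML. The document supports neither. Unmasking depends on what participants know, and nothing in the text fixes how often early retreatment will occur or which way participants' effort would shift.

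**Conclusion.** The point holds as a gap in the sham procedure. For the one-line and >10% edema triggers, the protocol specifies repeat SML and no matching sham, so as written a repeat session in an eye still better than 20/40 marks the SML arm. This could reveal the arm to a participant who knows the rule, ahead of the ETDRS primary outcomes.

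Its reach is limited to eyes entering at 20/25 or better for the acuity trigger and to eyes still better than 20/40 for the edema trigger. It can arise at any of 4 scheduled follow-up visits before month 12 and 8 before month 24, and at the return visit within 28 days. The size and direction of any bias cannot be derived.

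The conclusion rests on three assumptions: that participants are meant to be masked, which the sham implies; that some participants know or learn the rule; and the reading of the acuity steps given above. It is a point that should be corrected, because the remedy is cheap. It is not evidence that the trial fails. Confidence is medium, since the frequency of early retreatment is unknown.

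**What to change.** Extend the existing early rule to both arms. Suggested wording: *An eye in either arm that loses 1 or more ETDRS lines, or whose edema increases by more than 10%, may have a repeat session of its assigned procedure (SML or sham) at any later visit, including the return visit within 28 days, if the treating physician so decides.*

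The triggers and the physician's discretion stay as they are. The rule must cover every later visit. If sham were repeated only at the scheduled visits, the mismatch would remain at the 28-day return visit.

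The cost is one clause of protocol wording and a few extra sham set-ups. Each is the day-0 set-up without laser, done at a visit the participant already attends, and is a small burden on that participant. The number of repeat sessions may still differ between arms if the disease behaves differently under SML. What the change secures is that a repeat session no longer identifies the arm by rule.

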**10) Data and Specimen Banking**

All data will be stored on secured network drives at UC Davis and information properly de-identified (see below).

**11) Data Management and Confidentiality**

Captured OCT images and microperimetry reports will be analyzed by the UC Davis Reading Center in a masked fashion. Data analysis will be performed *by study staff, and standard statistical methods* will be used in the analysis of data collected. Subjects will be de-identified via the use of a separate secure document correlating subjects' UC Davis medical record numbers with a study ID assigned for the sole purpose of this study. Recorded data will be stored in a password protected excel file. Only the investigators will have access to these files. All study personnel will be Biomedical and GCP CITI certified and will be maintained by the research coordinating staff.

**12) Provisions to Monitor the Data to Ensure the Safety of Subjects**

Study data will be analyzed with the assistance of a CTSC biostatistician to determine if any safety concerns exist in respect to disease progression between the treatment arm and the sham arm. Analysis will be performed at the timepoint when 12-month follow-up data has been

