## **PROTOCOL TITLE: Micropulse for suppression of diabetic macular edema “PULSE STUDY”**

acquired from at least 10 eyes randomized to each group (laser treatment and sham). A summary of the findings will be prepared and utilized to determine if changes in study conduct or study termination is necessary.

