The risks associated with the use of subthreshold micropulse diode laser are much reduced compared to the standard continuous wave laser which is used in the treatment of retinal edema with visual acuity that is equal to or worse than 20/40 on the Snellen chart. Standard continuous wave focal laser treatments are associated with risks including early and late visual loss aggravation of macular edema (ME) sub-retinal fibrosis, choroidal neovascularization, visual field loss, loss of color vision, metamorphopsia, and progressive expansion of the laser scars into the fovea. However, the use of the subthreshold micropulse diode laser limits these standard risk factors by utilizing lower energy intensity and its “chopped” delivery method. Multiple studies have demonstrated the safety of subthreshold micropulse laser compared to standard continuous wave laser in the treatment of macular edema using various imaging modalities. There have been no detectable changes noted in eyes treated with subthreshold micropulse diode laser on OCT, fluorescein angiography (FA) or fundus autofluorescence (FAF). This has also been corroborated by histologic studies in which SML was noted to treat tissue without damage to the neurosensory retina. Others have also demonstrated repeatability of SML treatment without detectable structural or functional damage. In a prospective randomized clinical trial, Vujosevic et al. compared the safety of SML versus modified ETDRS green laser photocoagulation. They have shown that retinal sensitivity increased, and fundus autofluorescence imaging revealed no changes at one year follow up in eyes with DME even after retreatment with SML, whereas those treated with standard continuous wave laser revealed areas of hyperautofluorescence and decreased retinal sensitivity. The mean number of treatments was 2.03±0.75 in the SML group. Moreover, Luttrull et al. have shown that 15 out of 39 eyes with DME and visual acuity better than 20/40 treated with SML required retreatment, yet no

**PROTOCOL TITLE: Micropulse for suppression of diabetic macular edema  
“PULSE STUDY”**

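### The only review that can change or stop the trial is limited to disease progression, so possible laser injury that does not show as progression is outside its remit

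*Protocol*

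**What the plan says.** Section 12, whose title concerns the safety of subjects, provides for one analysis with a biostatistician's help. Its purpose is "to determine if any safety concerns exist in respect to disease progression between the treatment arm and the sham arm". It takes place once 12-month data exist for at least 10 eyes per group, and its summary is to be "utilized to determine if changes in study conduct or study termination is necessary". The protocol gives no other rule for changing or stopping the study.

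In section 8 the first primary outcome is the "Proportion of patients with vision loss to 20/40 or worse on ETDRS testing on two visits", and the second is the time to that loss. The last secondary outcome is "Any safety concerns documented during the study", with no mention of section 12.

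Section 9 schedules examination, OCT and microperimetry at nine follow-up visits. On retreatment it says "Patients in the treatment arm are eligible for repeat SML laser at any subsequent visit if there is any decline in vision" (one or more ETDRS lines) or if edema increases by more than 10%, as the physician judges. It also says "If vision declines to 20/40 or worse at any study visit, patients in the treatment arm will undergo repeat treatment with SML laser".

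Section 14 lists harms of standard continuous-wave focal laser, among them "visual field loss, loss of color vision, metamorphopsia, and progressive expansion of the laser scars into the fovea". It says that micropulse delivery limits these risks.

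**The concern.** A safety review should be able to see the harms that the intervention might cause. The intervention here is a laser applied to the macula of eyes that still see 20/32 or better, and sections 4 and 5 hypothesize that it will preserve vision. Progression is therefore what the laser is expected to reduce. A review limited to progression asks the efficacy question under a safety title.

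Two consequences follow. A laser arm with less progression could pass the review whatever else was found in its eyes. And an excess of progression in untreated sham eyes would be reported as the safety finding, with nothing said about the laser itself.

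This point concerns which events the review counts. It does not depend on the review's timing, error rate or masking.

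**Working it through.** There is no stated figure to reproduce. The check is to take what could be found in an eye and ask what section 12 does with it.

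| Finding | Recorded under section 9? | Treatment by the section 12 remit |
|---|---|---|
| New scotoma in a laser eye, acuity and thickness unchanged | Yes, microperimetry | Outside: not progression on any ordinary reading |
| Visible scar or other structural change in a laser eye, no acuity loss, no thickening | Yes, examination or OCT | Outside, for the same reason |
| Laser injury that lowers acuity | Yes, ETDRS testing | May enter, but as progression, not as a separate laser event |
| Macular edema worsens in a sham or laser eye | Yes | Inside |

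The first two rows are the gap in scope. The third is a gap in attribution.

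**Eyes concerned.** Section 7 plans 36 eyes at 2:1: 36 × 2/3 = 24 laser and 36 × 1/3 = 12 sham. Section 9 puts one eye in each arm when both are eligible, so if every patient were bilateral the split would be 36/2 = 18 and 18. Laser-exposed eyes thus number 18 to 24.

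**The third row at the plan's own rates.** Section 7 assumes 40% vision loss under sham and 15% under laser. With 24 laser eyes the expected losses are 24 × 0.15 = 3.6. The laser arm matches the sham proportion only at 24 × 0.40 = 9.6. If the design assumptions held, 9.6 − 3.6 = 6 further laser eyes could lose vision through injury before the laser arm looked no better than sham. This illustrates why a pooled count cannot separate the two causes. It does not forecast injury.

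**Relevance of laser injury.** Section 14 says that micropulse limits the continuous-wave risks; it does not say that they are abolished. Section 9 also uses a continuous-wave test spot, with power raised until a faint tissue effect can be seen, before the micropulse power is set at four times that level.

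**Links to the review.** The section 8 safety outcome, the follow-up tests in section 9 and the masked reading of OCT and microperimetry in section 11 all exist. None is named as an input to section 12.

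**The case against.** The strongest reply is that safety is already observed and that progression is a proper safety question. Both parts stand. Examination, OCT and microperimetry are repeated throughout, and section 8 has a safety outcome. Section 14 places the sham arm's risk at a fall to 20/40 or worse, so comparing progression between arms protects untreated eyes. A full event list could also sit in a statistical analysis plan that is not shown. But the protocol itself states the remit, and states it narrowly; that is more than a detail left for later.

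A reader might infer four stronger things that the protocol does not support:

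- **That sections 9 and 14 contradict each other**, because signs that prompt more laser are also listed as laser harms. Section 14 attributes those harms to standard continuous-wave treatment and cites studies with no detectable change after micropulse. Section 5 says the same of scarring and neovascularization. The test spot is continuous-wave, but is placed more than 2 DD from the foveal center.
- **That worsening leads only to more laser.** The first retreatment route is discretionary. An eye at 20/40 or worse must return within 28 days; if the loss is confirmed it is a treatment failure and other treatments are open to it.
- **That no injured eye would count.** Progression is undefined, and acuity is among the study data, so injury that lowers acuity could enter the comparison.
- **That the harm can be sized.** Any per-eye injury rate would be invented. Setting ten scheduled visits against the cited mean of 2.03 sessions compares a two-year theoretical maximum with a one-year average.

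**Conclusion.** The point holds as a defect of scope. The one review able to change or stop the trial is worded around disease progression, and the protocol's own safety outcome is not connected to it. Possible laser injury without acuity loss or edema worsening is outside the remit. Injury with acuity loss may be counted but would not be distinguished from macular edema progression.

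The defect bears on the 18 to 24 eyes expected to receive laser. How many of them might be injured cannot be said from the protocol. Equating progression with the efficacy outcome is an inference from an undefined term, though a close one, since vision loss to 20/40 or worse is the protocol's nearest measure. The conclusion does not require micropulse laser to be harmful, only that the review should be able to see it if it is.

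**What to change.** In section 12, keep disease progression, say how it is measured, and add the section 8 safety outcome to the review: ocular adverse events and possible laser-related findings from the examination, OCT and microperimetry already performed. Tabulate these by arm and by cumulative number of micropulse sessions. In section 8, state that this outcome feeds the section 12 review. Progression should not be removed, since that would take away the protection it gives sham eyes.

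The sponsor should also reconcile sections 9 and 12 on how documented safety findings bear on the review and on repeat laser. No clinical rule is proposed here.

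The cost is a rewording and one extra safety table. Visits, measurements and reviewers stay the same. Fundus autofluorescence is named at baseline but not in the follow-up list, so the table does not rely on it.
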